5 STUDY POPULATION

5.1 Participant Inclusion Criteria

A **Dental Health Care Worker** must meet all of the following criteria to be eligible to participate in the study:

- Be 18 years or older
- Be a National Dental PBRN member dentist or work in a dental office with a National Dental PBRN member dentist who consents to study participation
- Be able to understand the informed consent.
- Provide signed and dated informed consent form
- Be able to understand all instructions for data collection instruments
- Be willing and able to comply with all study procedures, including COVID-19 testing, and be available for the duration of the study

A **Patient** must meet all of the following criteria to be eligible to participate in the study:

- Be 18 years or older
- Be able to understand the informed consent.
- Have a computer or electronic tablet with internet access
- Able to complete consent and questionnaire on a computer or electronic tablet
- Provide signed and dated informed consent form
- Be able to understand all instructions for data collection instruments
- Be willing and able to comply with all study procedures, including having a COVID-19 test performed

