5.3 Strategies for Recruitment and Retention

Target Sample Size: 40 dental care health workers and 80 patients.

Target Sample Size by Gender, Race, Ethnicity, and Age: Study population will be drawn from National Dental PBRN dentist members, their co-workers and patients seen in their office. Any adult 18 years and older meeting the inclusion criteria and not meeting any exclusion criteria will be eligible to participate. It is expected that the mix of gender, race and ethnicity will reflect the patient mix of the participating dental offices.

Study Population: The DHCW study population will be dentists, hygienists, assistants and office staff who work in an office with a National Dental PBRN member dentist. The patient study population will be drawn from the dental practice with the National Dental PBRN member dentist.

Inclusion of Women and Minorities and Individuals of All Ages:

Women: Women will be included in this study.

Minorities: Minorities will be included in this study.

Recruitment Strategies: Four (4) National Dental PBRN practitioners who have 4 or more DHCW in their office will be recruited to participate by the National Dental PBRN Node Coordinator. The Node Coordinator will then recruit DHCWs within the practice to participate. If a practice is unable to consent at least 5 DHCWs, the practice will not participate in the study. Another National Dental PBRN practice will be recruited to participate.

Patients will be sent a letter about 4 weeks prior introducing the study by the PBRN practitioner. The PBRN practitioner or PBRN investigators in the office will reach out to patients by phone about 2 weeks prior to the dental visit. The study will be explained and if the patient is interested, an e-mail link will be sent which will allow the patient to review the informed consent. A phone number will be provided to answer questions.

Recruitment Protocol (All Study Groups):

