As this is a feasibility study, reviews of surveys and case reports to ensure completeness will not be completed, rather the number/percentage of incomplete surveys and forms will be analyzed as an outcome measure. Consent forms will be reviewed for completeness at the mid-study visit for DHCW subjects and as part of the end-of-visit survey for patient subjects.

Data Management Controls

REDCap is a rich system which enables privileging, required data element entry and required data validation to be embedded into daily operations.

- **Privileging:** Every study staff member will be assigned a role which carries specific read/write/edit/delete privileges. Staff member will be assigned a role providing minimal rights sufficient to perform his/her responsibilities.
- **Structured Data:** Whenever possible, data will be collected via structured data responses rather than free-text. Structured data requires a respondent to check a valid response.
- **Data Validation:** Data fields will be established limiting responses to those that are reasonable. For example, year of birth would have a range of 2002 (corresponding to age 18 – the youngest

eligible) to 1920 (corresponding to age 100 – more than sufficient to cover the age range of individuals having impacted 3rd molars extracted.)

- **Required Fields:** Whenever appropriate, fields have been made required so as to ensure completed forms and questionnaires.

Structured responses are required for the CRFs so only valid responses can be recorded. In addition, REDCap has been programmed with all responses being required at time of completion which will trigger an error message, but subjects can save their responses without all responses being completed. Validation rules are employed where possible.

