15.2 Data Capture Methods

Other than the Testing Case Report, all data for the study be electronically captured. Various devices will be used including:

- Laptop and desktop computers to complete surveys and forms directly into REDCap, the electronic data capture system for the study
- iPads to complete surveys, forms and capture electronic signatures directly into REDCap
- Bar code scanner to label study specimens

Patients will use their own computer or personal electronic device to sign the consent form and answer the pre-visit survey. DHCW will use their own computer, electronic device, an office computer electronic device or the study provided electronic pads for consents. All other forms and surveys to be completed DHCW or patient subjects by using study provided electronic pads.

REDCap will be used to collect and maintain all study data.

	DHCW Method of Collection	DHCW Entered By Whom	PATIENTS Method of Collection	PATIENTS Entered by Whom
Surveys	Survey administered via REDCap with responses entered directly into REDCap	By study participant on office iPad	Survey administered via REDCap with responses entered directly into REDCap	By study participant on computer or other electronic device at home
Triage Survey Case Report	Survey administered via REDCap form with responses entered directly into REDCap	By PBRN Practitioner or Investigator designee	REDCap form	By PBRN Practitioner or Investigator designee
POC Test Results Case Report	Data from Veritor Reader or Abbott COVID-19 Ag Card	By PBRN Practitioner or Investigator designee	Data from Veritor Reader or Abbott COVID-19 Ag Card	By PBRN Practitioner or Investigator designee
PCR Test Results Case Report	Data entered directly of e-mail of results into REDCap Form upon receipt of secure e-mail from lab	Rutgers PI, Chief of Protocol or Designee	Data entered directly into REDCap Form upon receipt of secure e-mail from lab	Rutgers PI, Chief of Protocol or Designee
ELISA Antibody Test Results Case Report	Data entered directly from e-mail of results into REDCap Form upon receipt of secure e-mail from lab	Rutgers PI, Chief of Protocol or Designee	Data entered directly into REDCap Form upon receipt of secure e-mail from lab	Rutgers PI, Chief of Protocol or Designee

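### The REDCap birth-year check (1920 to 2002) comes from a third-molar study and is fixed to 2020, so from 2021 it rejects the true birth year of eligible 18-year-olds; device wording in 5.1 and 15.2 also differs

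*Combined protocol and SAP*

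**What the plan says.** Section 13 (Data Management Controls, Data Validation) states the principle that "Data fields will be established limiting responses to those that are reasonable". Its example is that "year of birth would have a range of 2002 (corresponding to age 18", running back to 1920 for age 100, a span described as "more than sufficient to cover the age range of individuals having impacted 3rd molars extracted".

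The same section says that only valid responses can be recorded on the case report forms. It also says that an unanswered required item triggers an error message, yet "subjects can save their responses without all responses being completed". Surveys and case reports will not be reviewed for completeness, because the share left incomplete is itself an outcome.

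Age eligibility is set elsewhere. Section 5.1 requires age 18 or older and gives no upper limit, and Section 5.3 adds: "Any adult 18 years and older meeting the inclusion criteria and not meeting any exclusion criteria will be eligible to participate".

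On devices, one patient inclusion criterion in Section 5.1 is "Have a computer or electronic tablet with internet access", and the next requires the ability to use such a device for consent and questionnaire. Section 15.2 says: "Patients will use their own computer or personal electronic device to sign the consent form and answer the pre-visit survey". The table in 15.2 also allows some other electronic device at home.

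**The concern.** A fixed calendar year stands in for an age only during the year for which it was set. The third-molar justification shows that the text was written for another study, so the limits were probably never checked against this study's enrolment period.

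If enrolment reaches 2021, some adults who meet the age criterion cannot enter their own birth year. What is at stake is data quality and one declared outcome. Sections 3.0 and 11.1 count survey completeness as a feasibility measure, and Section 3.0 says that its purpose is to refine the REDCap instruments. A blank forced by the form would be read as a participant's failure to complete. A false year would pass unnoticed.

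The device wording raises a separate, smaller question. An office that follows 5.1 would decline a patient who has only a smartphone, whereas an office that follows 15.2 might accept that patient. Patient willingness, the ratio of those agreeing to those asked, could then differ between offices for reasons of wording alone.

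**Working it through.** **Inputs**
- Birth-year limits 2002 and 1920, with stated ages 18 and 100 (Section 13).
- Age 18 or older, no upper limit (Section 5.1).
- Six months to complete enrolment and no calendar start date (Protocol Summary). The latest calendar date in the text is a reference dated 27 May 2020 (Section 17).
- 80 patients and 40 dental health care workers, 120 in all (Section 5.3).
- Assumption, not from the documents: each birth year holds 0.5% to 2% of participants.

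**Step 1: reproduce the plan's figures.** Reference year = birth year + stated age. 2002 + 18 = 2020 and 1920 + 100 = 2020. Both limits agree with 2020 and with no other year.

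**Step 2: move the consent year.** The youngest birth year that can contain an 18-year-old is the consent year minus 18.
- 2020: 2020 − 18 = 2002. Nobody aged 18 to 100 is rejected.
- 2021: 2021 − 18 = 2003. Birth year 2003 is rejected.
- 2022: 2022 − 18 = 2004. Birth years 2003 and 2004 are rejected.
- 2023: 2023 − 18 = 2005. Birth years 2003 to 2005 are rejected.

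At the other end, only people born before 1920 are rejected.

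**Step 3: would enrolment reach 2021?** Share of a six-month window falling in 2021, by assumed start date:
- 1 July 2020 or earlier: 0%
- 1 August 2020: 31 of 184 days = 17%
- 1 October 2020: 90 of 182 days = 49%
- 1 December 2020: 151 of 182 days = 83%

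Two features make a later start plausible without proving it. Section 5.2 excludes people from a feasibility study already conducted at Rutgers, and the surveys in Section 7 ask about vaccination.

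**Step 4: size.** Expected number affected = n × share, for one rejected birth year.
- 80 patients: 80 × 0.005 = 0.4 to 80 × 0.02 = 1.6
- All 120: 120 × 0.005 = 0.6 to 120 × 0.02 = 2.4
- Chance of at least one among 120: 1 − 0.995^120 = 45% to 1 − 0.98^120 = 91%

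These figures apply if all consents fall after 2020 and the whole birth year has turned 18. For consent early in 2021, when few people born in 2003 are yet 18, the number is lower.

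**Step 5: where the check acts.** Section 7 puts demographics in the Patient Pre-Visit Survey, which opens after consent is completed, and in the worker start-of-study survey, also after consent. If birth year is one of those demographic items, as seems natural, a rejected value affects someone already enrolled. That person can save the form with the item empty or type an accepted year.

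**Step 6: device wording side by side.** Section 5.1 names two device types. Section 15.2 names a computer or a broader class that includes tablets and could include phones. No section mentions smartphones.

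**The case against.** The strongest reply is that the range is only an illustration in a quality-control section. Eligibility is governed by Section 5.1 and, for those under 18, by Section 14.4, and the field comes after consent. A reader might infer that eligible adults are shut out of the study. The documents do not support that: a rejected year produces a blank or wrong field in an enrolled participant.

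A reader might also infer that a minor could be enrolled, since in 2020 a person born late in 2002 may still be 17 and would pass the check. That does not follow either, because this check is not what enforces the age rule.

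The effect also depends on a start date that the documents do not give. For consent in 2020 the limits do no harm.

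On devices, the computer-or-tablet rule is itself an inclusion criterion, and Section 5.3 makes eligibility conditional on the inclusion criteria. Smartphone-only patients are therefore not people whom the protocol calls eligible. Nor do the two sections strictly contradict each other, since a tablet is a personal electronic device. The documents give no smartphone-only share, so no number of excluded patients can be stated.

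All of this stands and limits the point. It does not rescue a validation rule that is wrong from 2021 and is justified by another study's population. Nor does it settle which device wording the offices should follow.

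**Conclusion.** The birth-year check holds as a form defect of small size. It is correct for 2020 only, and for any later consent it rejects true values from adults who meet the age criterion. On the assumed 0.5% to 2% per birth year, about 0 to 2 participants are affected for each rejected year.

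The conclusion rests on three conditions: some consent takes place in 2021 or later, the range is built as a limit that refuses values (as Section 13 describes) rather than as a warning, and birth year is a survey item after consent. If all consent fell in 2020, only the misplaced third-molar text would remain.

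The consequence is a form-caused blank or a false birth year. A blank counts against a declared feasibility outcome, and the planned absence of completeness review makes its cause harder to see.

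The device point is secondary. The wording in 5.1 is narrower than in 15.2, and aligning it matters only so that offices screen alike and the willingness ratio has one meaning.

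**What to change.** - In Section 13 and in REDCap, replace the fixed range with a check tied to the consent date: either age at consent of 18 or older, or an upper birth-year limit of consent year minus 18 (2003 for 2021, 2004 for 2022). The year-only version is a plausibility check and leaves age eligibility to Section 5.1.
- Drop the 1920 floor or make it a warning that can be overridden, since 5.1 sets no upper age.
- Delete the third-molar justification.
- Reconcile the device wording in Sections 5.1 and 15.2, stating whether a smartphone qualifies, and record how many patients are declined for lack of a qualifying device.

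The cost is one REDCap setting, a line or two of protocol text, one screening-log item, and sIRB approval of the amendment under Section 14.2. If smartphones are allowed, the survey layout must be checked on a phone. No change is needed for the end-of-visit surveys, because Section 15.2 already provides study pads for them.

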14 ETHICS/PROTECTION OF HUMAN SUBJECTS

14.1 Ethical Standard

The investigator will ensure that this study is conducted in full conformity with the principles set forth in The Belmont Report: Ethical Principles and Guidelines for the Protection of Human Subjects of Research, as drafted by the US National Commission for the Protection of Human Subjects of Biomedical and Behavioral Research (April 18, 1979) and codified in 45 CFR Part 46 and/or the ICH E6.

14.2 Institutional Review Board

The protocol, informed consent form(s), recruitment materials, and all participant materials will be submitted to the sIRB for review and approval. Approval of both the protocol and the consent form(s) must be obtained before any participant is enrolled. Any amendment to the protocol will require review and approval by the sIRB before the changes are implemented in the study.

14.3 Informed Consent Process

Informed consent is a process that is initiated prior to the individual agreeing to participate in the study and continues throughout study participation. Extensive discussion of risks and possible benefits of study participation will be provided to participants and their families, if applicable. A consent form describing in detail the study procedures and risks will be given to the participant. Consent forms will be sIRB-approved, and the participant is required to read and review the document or have the document read to him or her. The investigator or their investigator designee will explain the research study to the participant and answer any questions that may arise.

All DHCWs and patient participants will review and electronically sign the informed consent document prior to any study-related assessments or procedures. For LAB and POC patient subjects, an electronic consent and signature will be obtained before the Pre-Visit-Triage survey is completed.

Participants will be given the opportunity to discuss the study with their surrogates or think about it prior to agreeing to participate. They may withdraw consent at any time throughout the course of the study. A copy of the signed informed consent document will be given to participants for their records. The rights and welfare of the participants will be protected by emphasizing to them that the quality of their clinical care will not be adversely affected if they decline to participate in this study.

The consent process will be documented in the clinical or research record.

14.4 Exclusion of Women, Minorities, and Children (Special Populations)

Women and minorities will be eligible to participate. Children less than 18 years will not be able to participate.

14.5 Subject Confidentiality

Subject confidentiality is strictly held in trust by the investigators, study staff, and the study sponsor(s) and their agents. This confidentiality is extended to cover testing of biological samples and genetic tests in addition to any study information relating to participants.

The study protocol, documentation, data, and all other information generated will be held in strict confidence. No information concerning the study, or the data will be released to any unauthorized third party without prior written approval of the study sponsor.

The study monitors or other authorized representatives of NIDCR may inspect all study documents and records required to be maintained by the investigator, including but not limited to, medical records (office, clinic, or hospital) for the study participants. The clinical study site will permit access to such records.

Certificate of Confidentiality

To further protect the privacy of study participants, the Secretary, Health and Human Services (HHS), has issued a Certificate of Confidentiality (CoC) to all researchers engaged in biomedical, behavioral, clinical, or other human subjects research funded wholly or in part by the federal government. Recipients of NIH funding for human subjects research are required to protect identifiable research information from forced disclosure per the terms of the NIH Policy (<https://humansubjects.nih.gov/coc/index> - Certificates of Confidentiality (CoC) – Human Subjects). As set forth in [45 CFR Part 75.303\(a\)](#) and [NIHGPS Chapter 8.3](#), recipients conducting NIH-supported research covered by this Policy are required to establish and maintain effective internal controls (e.g., policies and procedures) that provide reasonable assurance that the award is managed in compliance with Federal statutes, regulations, and the terms and conditions of award. It is the NIH policy that investigators and others who have access to research records will not disclose identifying information except when the participant consents or in certain instances when federal, state, or local law or regulation requires disclosure. NIH expects investigators to inform research participants of the protections and the limits to protections provided by a Certificate issued by this Policy.

NIH Data Sharing Policies

As described in section 17, it is NIH policy that the results and accomplishments of the activities that it funds should be made available to the public (see <https://grants.nih.gov/policy/shring.htm> - NIH Sharing Policies and Related Guidance on NIH-Funded Research Resources). PIs and funding recipient institutions will ensure that all mechanisms used to share data include proper plans and safeguards to protect the rights and privacy of individuals who participate in NIH-sponsored research.

14.6 Future Use of Stored Specimens and Other Identifiable Data

No residual specimens will be maintained after this project is completed. All Identifiable data will be destroyed 6 years after the study is completed.

15 DATA HANDLING AND RECORD KEEPING

The study PI is responsible for ensuring the accuracy, completeness, legibility, and timeliness of the data reported. All source documents should be completed in a neat, legible manner to ensure accurate interpretation of data. The investigators will maintain adequate case histories of study participants, including accurate case report forms (CRFs), and source documentation.

15.1 Data Management Responsibilities

The PIs in collaboration with the NCC will review reports of data completeness and accuracy as well as protocol compliance on an ongoing basis throughout the study.

15.2 Data Capture Methods

Other than the Testing Case Report, all data for the study be electronically captured. Various devices will be used including:

- Laptop and desktop computers to complete surveys and forms directly into REDCap, the electronic data capture system for the study
- iPads to complete surveys, forms and capture electronic signatures directly into REDCap
- Bar code scanner to label study specimens

Patients will use their own computer or personal electronic device to sign the consent form and answer the pre-visit survey. DHCW will use their own computer, electronic device, an office computer electronic device or the study provided electronic pads for consents. All other forms and surveys to be completed DHCW or patient subjects by using study provided electronic pads.

REDCap will be used to collect and maintain all study data.

	DHCW Method of Collection	DHCW Entered By Whom	PATIENTS Method of Collection	PATIENTS Entered by Whom
Surveys	Survey administered via REDCap with responses entered directly into REDCap	By study participant on office iPad	Survey administered via REDCap with responses entered directly into REDCap	By study participant on computer or other electronic device at home
Triage Survey Case Report	Survey administered via REDCap form with responses entered directly into REDCap	By PBRN Practitioner or Investigator designee	REDCap form	By PBRN Practitioner or Investigator designee
POC Test Results Case Report	Data from Veritor Reader or Abbott COVID-19 Ag Card	By PBRN Practitioner or Investigator designee	Data from Veritor Reader or Abbott COVID-19 Ag Card	By PBRN Practitioner or Investigator designee
PCR Test Results Case Report	Data entered directly of e-mail of results into REDCap Form upon receipt of secure e-mail from lab	Rutgers PI, Chief of Protocol or Designee	Data entered directly into REDCap Form upon receipt of secure e-mail from lab	Rutgers PI, Chief of Protocol or Designee
ELISA Antibody Test Results Case Report	Data entered directly from e-mail of results into REDCap Form upon receipt of secure e-mail from lab	Rutgers PI, Chief of Protocol or Designee	Data entered directly into REDCap Form upon receipt of secure e-mail from lab	Rutgers PI, Chief of Protocol or Designee

All study data will be centrally stored on the Rutgers REDCap data management system, and study-related documentation will be maintained on RSDM PREDICT Box drive. REDCap is a secure web application which is password protected and compliant with 21 CFR Part 11. Study data and documentation will be available to the study PI and core personnel in real time, per allowable permissions.

